10.2.2 Tissue

Breast tissue fixation with neutral buffered formalin for 4–48 hours has been shown to be adequate. Thus, when tissue is fixed in neutral buffered formalin, IHC for Ki-67 is robust across a wide range of fixation times. Tissue handling guidelines that are already in place for ER (8–72 hours of neutral buffered formalin fixation) are therefore more than adequate for Ki-67. Once tissue is properly fixed and embedded in paraffin, antigenicity is well preserved, potentially for decades.

FFPE sections from breast tumor (baseline and surgical specimens) will be cut locally by each site and shipped for **centralized evaluation of immunohistochemical biomarker analyses** at IEO. Six consecutive 5-micron thick sections will be cut from each FFPE block and mounted on charged slides, preferably within 7 days prior to shipping.

Flash frozen specimen from surgical resections (minimal wet weight: 200 mg) both from the tumor and the macroscopically negative normal tissue will be collected within 20-30 minutes, frozen on liquid nitrogen and stored in freezer at -80°C.

There could be some cases of insufficient tumor tissue available to be snap frozen (in situ histology, small size of invasive cancer, etc). However, any effort should be made to collect and freeze normal breast tissue for secondary endpoint measurements.

Note for the US Sites: Additional **Flash Frozen Breast Tumor tissue from the surgical specimen** (minimal wet weight: 50 mg) will be collected at the US Sites only for Proteomic Biomarker Discovery at the Proteomics Shared Resource, Herbert Irving Comprehensive Cancer Center, Columbia University Medical Center. This specimen is only collected by the US sites, stored in local freezers at -80°C until the end of the study, and shipped to CUMC per the shipping instructions in the Manual of Operations and Procedures.

10.3 Shipping Instructions

In order to keep shipping costs at an affordable level, Participating Centers are requested to store blood samples at -80°C until pick-up by a courier will be arranged by and to the Central Laboratory at the Division of Cancer Prevention and Genetics, European Institute of Oncology in Milan, Italy. Samples will be shipped on dry ice in compliance with the International Air Transport Association (IATA) Dangerous Goods Regulations. Specific instructions about specimen shipping will be provided in a dedicated Manual of Operations and Procedures.

Tissue specimens will be stored locally until shipment the Central Laboratory at the Division of Cancer

Prevention and Genetics, European Institute of Oncology in Milan, Italy. Storage and shipment instructions are outlined in the Manual of Operations and Procedures.

Note to the US Sites: Tissue collected for Proteomic Biomarker Discovery will be stored locally and shipped to the Proteomics Shared Resource, Herbert Irving Comprehensive Cancer Center, Columbia University Medical Center. Storage and shipment instructions are outlined in the Manual of Operations and Procedures.

10.4 Specimen Banking

Leftover specimens will be stored at IEO Central Biobank for optional studies.

Biologic specimens collected during the conduct of the trial that are not used during the course of the study will be considered deliverables under the contract and thus the property of the NCI. At study completion, NCI reserves the option to either retain or relinquish ownership of the unused biologic specimens. If NCI retains ownership of specimens, the Contractor shall collect, verify and transfer the requested biologic specimens from the site to a NCI-specified repository or laboratory at NCI's expense.

11. REPORTING ADVERSE EVENTS

DEFINITION: AE means any untoward medical occurrence associated with the use of a drug in humans, whether or not considered drug related. An AE can therefore be any unfavorable and unintended sign, symptom, or disease temporally associated with participation in a study, whether or not related to that participation. This includes all deaths that occur while a participant is on a study.

Please note that all abnormal clinical laboratory values that are determined to be of clinical significance based on a physician's assessment are to be reported as AEs. Those labs determined to be of no clinical significance or of unknown clinical significance (per the physician's assessment) should not be reported as AEs. Any lab value of unknown clinical significance should continue to be investigated/followed-up further for a final determination, if possible.

A list of AEs that have occurred or might occur (Reported Adverse Events and Potential Risks) can be found in §6.2, Pharmaceutical Information, as well as the Investigator Brochure or package insert.

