3. SUMMARY OF STUDY PLAN

We will conduct a multicenter, pre-surgical double-blind non-inferiority phase IIb study in which participants will be randomized to receive either exemestane 25 mg/day or 25 mg/ three times a week or a single dose of 25 mg/week for a minimum of 4 up to 6 weeks.

A total of 180 post-menopausal women will be accrued; 60 per arm, enrolled in 35 months and treated for a minimum of 4 up to 6 weeks.

Participants will be histologically-confirmed ER-positive (ER $\geq 10\%$) primary breast cancer patients who are candidates for breast surgery. Postmenopausal women younger than 76 years of age with cT₀₋₂, cN₀₋₁, M_x or women with larger tumors who refuse neo-adjuvant therapy before surgery are eligible. No previous treatment for breast cancer is allowed.

Complete physical exam and safety lab tests will be performed at baseline and at end of treatment (28+1, 35+1, 42+1 days). Phone contact will occur at day 1 and a week before surgery (+3 days).

Biomarkers: blood samples will be collected at baseline and the end of treatment (fasting blood for biomarkers will be collected prior to randomization and either on the day of surgery or the day before; fasting is strongly recommended but is not mandated), tissue samples will be collected from the diagnostic or research biopsy and at the time of surgery.

Duration of study will be four years: 35 months for accrual, 4-6 weeks of treatment, and one year for biomarkers measurement.

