6.2 Reported Adverse Events and Potential Risks

According to the UK SPC for 25 mg exemestane film-coated tablets from Actavis UK Ltd., the most commonly reported adverse events (AEs) by early breast cancer patients treated with exemestane were (in order of frequency): hot flushes (22%), arthralgia (18%) and fatigue (16%). AEs similarly or less commonly reported by early breast cancer patients treated with exemestane compared to tamoxifen were headache (14%), insomnia (13%), sweating increased (12%), gynecological disorders (11%), and dizziness (10%). Similar to early breast cancer, in advanced BC hot flushes were the most common AE (14%), followed by nausea (12%). Other common AEs ($\geq 1\%$ to $<10\%$) seen in clinical studies and postmarketing reports were: anorexia, alopecia, carpal tunnel syndrome, constipation, depression, diarrhea, dyspepsia, fracture, osteoporosis, other primary cancer, pain, paresthesia, peripheral edema,

pruritis, reduction in bone mineral density, rash, urticaria, vaginal haemorrhage, visual disturbance, and vomiting. Uncommon AEs ($\geq 0.1\%$ to $< 1\%$) were: acute generalized exanthematous pustulosis, asthenia, gastric ulcer, hepatitis (including cholestatic hepatitis, hepatic enzyme increased, blood bilirubin increased, and blood alkaline phosphatase increased), leucopenia, lymphocyte count decreased, somnolence, thrombocytopenia, and thromboembolism. Though rare, ischemic cardiac events were not significantly different with exemestane compared to tamoxifen (4.5% vs. 4.2%), including individual AEs hypertension (9.9% vs. 8.4%), myocardial infarction (0.6% vs. 0.2%), and cardiac failure (1.1% vs. 0.7%) (Full prescribing information in the SPC is available at: www.medicines.org.uk/emc/medicine/24704).

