7.5 Evaluation at Completion of Study Intervention

At the final visit, participants will undergo physical exam, vital signs, and anthropometric measurements (weight, waist measurement, hip measurement). These procedures may be done **within 7 days prior to surgery or on the day of surgery**. Do not repeat the height assessment at the Final Visit. Height measurement will be used from the baseline visit.

Blood tests for safety that do not require fasting may be done **within 7 days prior to surgery or on the day of surgery**:

- complete blood count (CBC), AST, ALT, Na, K, BUN, total bilirubin, Cl, Ca, alkaline phosphatase, and creatinine

All other procedures are performed the day of surgery or the day before surgery:

Fasting blood lab tests that are performed at the local lab (glucose, total cholesterol, HDL cholesterol and triglycerides). Fasting is strongly recommended, but is not mandated. Every effort should be taken to draw these labs fasting.

Fasting blood for biomarkers will be collected. Fasting is strongly recommended, but is not mandated. Every effort should be taken to draw these labs fasting.

The date and time of blood draw, the date and time of surgery, and the date and time of last pill intake will be recorded.

The use of concomitant medications, adverse events, compliance, and quality of life assessment will be assessed. Study agent will be collected. A review of agent diary will be performed.

Any kind of surgery will be allowed from simple lumpectomy to total mastectomy. Tissue samples will be collected from the surgical specimen and processed according to Section 10. A detailed Manual of Operations and Procedures will be implemented with the specific procedures for each specimen.

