13.5 Secondary Objectives, Endpoints, Analysis Plans

We will attempt to understand the mechanism of action of exemestane on the primary endpoint of the study. More specifically, we will assess the effects of exemestane on the secondary endpoint biomarkers to see whether the effects of different doses on the primary endpoint is through the secondary endpoint biomarkers or independent of them. This will entail exploratory analysis of the primary endpoint by the secondary endpoint biomarkers while accounting for the effect of treatment.

Secondary objectives:

- To assess safety and toxicity.
- To support the preventive activity of exemestane we will investigate the change in Ki-67 and PgR level on the tumor adjacent intraepithelial neoplasia and/or grossly benign tissue.
- To assess possible association of estradiol level with tissue and circulating biomarkers.
- To investigate possible pharmacogenetic markers.
- To assess drug levels on tissue samples.
- To investigate tissue and circulating proteomics profiling.

Secondary endpoints:

- Exemestane safety and toxicity will be evaluated at the clinic visit according to the Common Terminology Criteria for Adverse Events v4.0 (CTCAE) and by a self-administered Quality of Life questionnaire (MENQOL).
- Change in Ki-67 expression comparing pre-treatment versus post-treatment specimen to compare the antiproliferative effect among the different dosages.
- Serum drug measurements of exemestane and 17-dihydroxyexemestane at the end of treatment.
- Additional validated method of estradiol measurement. This method has a lower detection limit (1 pg/ml) than the CLIA certified estradiol test (Quest) and will serve as a quality control since it has proven to more effectively detect estradiol concentrations at the very low level, which is characteristic of older postmenopausal women.
- Serum concentrations of estrone, estrone-sulfate, will be measured by LC-MS/MS while androstenedione and testosterone will be measured at baseline and at surgery. Sex hormone binding globulin serum levels will be measured by a chemiluminescent microparticle immunoassay (CMIA) on the ARCHITECT *i* System (Abbott Laboratories, Weisbaden, Germany).
- Change in concentrations of insulin, glucose (HOMA index) and lipid profile (total cholesterol, HDL cholesterol and triglycerides) will be evaluated.

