- Adipokines: change in leptin and adiponectin serum concentrations will be analyzed and compared among the different treatments arms. These measurements will be performed by the use of commercially available enzyme linked immunoassays purchased from R&D systems (SPACE Import-Export Srl, Milan, Italy).
- Measurement of breast estradiol concentration in tumor and normal breast tissue at time of surgery.
- Centralized evaluation of ER, PgR, Her2 expression in tumor comparing pre-treatment levels (tru-cut biopsy) to post-treatment level expression (surgical specimen). Centralized evaluation of Ki-67 in adjacent intraepithelial neoplasia and or grossly benign tissue.
- Drug measurements of exemestane and 17-dihydroxyexemestane on frozen tissue samples, when available.
- Proteomic analysis will be performed with the new Fusion Tribrid mass spectrometer in [name] Shared Resource for the Herbert Irving Comprehensive Cancer Center (HICCC) at CUMC.
- To analyze the UGT2B17 gene we will use Taqman copy number variation assay (Life Technologies, Monza, Italy).
- Crown like structures in mammary fat tissue by IHC (CD68), comparing pre-treatment (tru-cut biopsy) versus post-treatment (surgical specimens).

Analysis plan

We will present full distributions and median values of circulating biomarkers, Ki-67, exemestane and 17-dihydroxyexemestane in tissue at baseline, after treatment and also of changes and percentage changes (with interquartile ranges) of all continuous variable, by arms. ANCOVA models will evaluate the associations of post values (after treatment) and changes from baseline by study arms adjusting for baseline values, explanatory variables and possible confounders (such as age and BMI). Normal distribution of residuals from full models will be checked and, if needed, a transformation will be considered.

For binary variables, when we need to assess differences in frequencies, Chi-squares tests and Odds ratios (ORs) will be calculated. Multivariate logistic models will be considered to assess differences between

arms, adjusting for possible confounders. We will report nominal P-values and we will highlight associations that meet a false discovery rate adjusted P less than or equal to .05 by the Benjamini and Hochberg method.

Analyses on secondary endpoints will be considered as exploratory since we will not have enough power to draw definitive conclusions.

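### Low-grade laboratory changes may be under-counted in the toxicity comparison, because a value counts only if a physician judges it clinically significant and no graded laboratory analysis is planned

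*Combined protocol and SAP*

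**What the plan says.** Section 6.2 lists, among adverse events in the 0.1% to below 1% class, "hepatitis (including cholestatic hepatitis, hepatic enzyme increased, blood bilirubin increased, and blood alkaline phosphatase increased), leucopenia, lymphocyte count decreased, somnolence, thrombocytopenia". The schedule in 7.1 measures the matching tests (blood count, AST, ALT, total bilirubin, alkaline phosphatase, creatinine and electrolytes) at baseline and once more at the final visit.

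Sections 8.2 and 13.5 define the safety endpoint: "Exemestane safety and toxicity will be evaluated at the clinic visit according to the Common Terminology Criteria for Adverse Events v4.0 (CTCAE"), together with the MENQOL questionnaire. Section 11 decides which laboratory values become adverse events. Those that a physician judges clinically significant do; for the rest, "Those labs determined to be of no clinical significance or of unknown clinical significance (per the physician's assessment) should not be reported as AEs". The sentence after that asks for values of unknown significance to be pursued to a final determination where this can be done. Section 11.1.5 applies the same judgement to follow-up.

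On analysis, 13.7 says only who is evaluable for toxicity. Section 13.5 promises full distributions and medians for circulating biomarkers, Ki-67 and drug levels, and "changes and percentage changes (with interquartile ranges) of all continuous variable, by arms".

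On timing, Section 3 states "Complete physical exam and safety lab tests will be performed at baseline and at end of treatment (28+1, 35+1, 42+1 days"), whereas 7.5 says "Blood tests for safety that do not require fasting may be done" within 7 days before surgery or on the day, as does footnote 10 of 7.1.

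**The concern.** The endpoint uses a graded scale, but entry to it is decided by a judgement that is not tied to grade. Section 11.1.3 describes grade 1 as covering symptom-free, purely diagnostic findings for which no intervention is indicated. A physician could reasonably call such a finding not clinically significant, and it would then not be counted. The threshold may also differ between physicians at five sites in two countries.

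The route back for a value of unknown significance is thin. There is one post-baseline safety sample and no scheduled repeat. The call after surgery (7.6) goes only to women with an unresolved adverse event already reported and attributed to the agent.

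At stake is the laboratory part of the safety comparison between schedules: mild changes that are measured in every woman but may not reach the toxicity table.

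**Working it through.** The plan states no figure on this point, so there is none to reproduce. The check has four steps.

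**1. Can a mild laboratory change reach the toxicity result?**
- Measured: yes (7.1, 7.5).
- Gradable on the chosen scale: yes (11.1.3, grade 1).
- Counted as an adverse event: only after a judgement of clinical significance (Section 11).
- Counted by another planned analysis: not clearly. 13.7 has none. The list of variables in 13.5 does not name the safety tests, although its closing reference to all continuous variables could be read to include them.

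**2. What the documents' own rate implies.** With 60 women per arm and a rate of 0.1% to 1% for one event type (6.2; the upper limit is exclusive):
- expected events per arm: 60 × 0.001 = 0.06 to 60 × 0.01 = 0.6;
- chance of at least one: 1 − 0.999^60 = 5.8% to 1 − 0.99^60 = 45.3%.

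No recording rule makes events this rare comparable between arms. At 1% v 0.1%, power is about 0.3% (chi-square) even with complete counting. What can be lost is therefore mainly mild graded change, for which the documents give no rate.

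**3. What a common filter does.** Let p1 and p2 be the true proportions with a new graded change, and f the share recorded, equal in both arms:
- observed risk difference = f × (p1 − p2);
- observed risk ratio = (f × p1)/(f × p2) = p1/p2, unchanged.

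Illustration with assumed rates of 20% v 5%, 60 per arm, two-sided 0.05. Power is the summed binomial probability of all tables that reject:

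| f | Expected counts | Risk difference | Power, chi-square | Power, Fisher |
|---|---|---|---|---|
| 1 | 12 v 3 | 15.0 points | 73% | 63% |
| 0.75 | 9 v 2.25 | 11.25 points | 59% | 44% |
| 0.5 | 6 v 1.5 | 7.5 points | 39% | 23% |
| 0.25 | 3 v 0.75 | 3.75 points | 18% | 4% |

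Chi-square is the test named in 13.5; Fisher's exact test is shown because the lower rows have small counts. The risk ratio is 4 in every row. The odds ratio, which 13.5 also names, moves only a little: (0.20/0.80)/(0.05/0.95) = 4.75 at f = 1, and (0.05/0.95)/(0.0125/0.9875) = 4.16 at f = 0.25. Under other assumed rates, chi-square power falls between f = 1 and f = 0.25 from 46% to 5% (10% v 2%) and from 80% to 22% (30% v 10%).

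**4. Timing.** In a 28-day course with surgery on day 29, a draw 7 days before surgery comes after 21 of 28, 9 of 12 and 3 of 4 active tablets in arms 1, 2 and 3, which is 75% in each. For the 35-day and 42-day courses it is 28/35 = 80% and 35/42 = 83%. Section 3 describes the same sample as taken at end of treatment.

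**The case against.** A reader might infer that values of unknown significance are simply discarded and that these harms will therefore be under-reported. The documents do not support that. Section 11 asks for such values to be pursued to a determination. The bar on recording events after surgery concerns new events; it does not prevent a later decision on a value drawn before surgery. No document gives the share of values filtered out, so under-counting is a likely direction and not a demonstrated result.

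A reader might also infer that the comparison between schedules is biased. Investigators are blinded (6.9), so the filter should act alike in all arms, and the expected risk ratio is preserved.

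Three further objections carry weight:
- The tolerability argument in 2.3 names symptoms, bone loss, musculoskeletal pain and quality of life. It names no hepatic or haematological effects, and symptom reporting does not pass through the laboratory filter.
- Section 13.5 promises full distributions, which would show extreme values if the safety tests are included.
- Secondary endpoints are declared exploratory.

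These points limit the importance of the concern. They do not remove the gap: the follow-up route has no scheduled sample or time limit, the safety tests are not named in 13.5, and a distribution of raw values is not a count of women whose grade worsened.

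**Conclusion.** The concern holds in a limited form. Low-grade laboratory changes may be under-counted in the CTCAE comparison, because recording depends on a physician's judgement and no planned analysis clearly grades the values already collected. The effect is on counts, absolute differences and precision; the expected risk ratio is unaffected if the filter is the same in all arms. The size is unknown. The power figures above rest wholly on assumed rates and recording shares, and show only that the loss is steep if many values are filtered. Changes judged clinically significant are still reported. This is a cheap improvement to an exploratory endpoint and does not touch the primary analysis.

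The mismatch between Section 3 and Sections 7.1 and 7.5 on the final safety sample is real but minor. The last quarter of dosing lies after that sample only in the shortest course with the earliest permitted draw.

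**What to change.** Add to 13.5 or 13.7: for AST, ALT, bilirubin, alkaline phosphatase, creatinine and the blood count, derive the CTCAE v4.0 grade from the recorded value and the local normal range in every treated woman with a sample, whatever the clinical-significance judgement. Tabulate baseline-to-final grade shifts and any worsening by arm, with differences from daily dosing and 95% confidence intervals, labelled exploratory. Shifts are needed because 4.1.3 admits women with bilirubin up to 2 times, and AST/ALT up to 1.5 times, the upper limit of normal. The reporting rule in Section 11 can stay.

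The cost is a paragraph of SAP text and one derived table per test, with no new visit or sample. Section 14.2.3 already collects normal ranges for laboratories listed on Form FDA 1572; the range would have to be obtained for any value from a laboratory not listed there. The downside is that more minor changes of doubtful relevance will appear in the safety report.

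Separately, reconcile Section 3 with 7.1 footnote 10 and 7.5 on when the final safety laboratory tests are drawn.

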11.1 Adverse Events

11.1.1 Reportable AEs

All AEs that occur after the informed consent is signed and baseline assessments are completed must be recorded on the AE CRF (paper and/or electronic) whether or not related to study agent.

11.1.2 AE Data Elements:

The following data elements are required for adverse event reporting.

- AE verbatim term
- NCI Common Terminology Criteria for Adverse Events version 4.0 (CTCAE v4.0) AE term (MedDRA lowest level term)
- CTCAE (MedDRA) System Organ Class (SOC)
- Event onset date and event ended date

- Treatment assignment code (TAC) at time of AE onset
- Severity grade
- Attribution to study agent (relatedness)
- Whether or not the event was reported as a serious adverse event (SAE)
- Whether or not the subject dropped due to the event
- Outcome of the event

